### Table 13: Time to death: comparison: 50/28mg versus CS3B sham control

Туре	Analysis Method	Analysis Population: further notes

## 6.4.9. Time to death or permanent ventilation (tracheostomy or ≥ 16 hours of ventilation/day continuously for > 21 days in the absence of an acute reversible event): comparison: 50/28mg versus 12 mg Group from 2328M203

Main and sensitivity analyses will be analyzed in the same way as similar secondary endpoint described in section 6.4.7.

Туре	Analysis Method	Analysis Population: further notes
Main Analysis	Log-rank test stratified by disease duration at Screening	ITT Set
Sensitivity Analysis	Cox proportional hazards with treatment and each subject's disease duration at Screening and baseline CHOP INTEND total score as terms in the model	ITT Set
	Log-rank test stratified by disease duration at Screening; by disease duration	ITT Set
	Log-rank test stratified by disease duration at Screening; by Baseline CHOP INTEND	ITT Set
	Joint rank using multiple imputation (MI)	PPS Set

Table 14: Time to death or permanent ventilation: comparison: 50/28mg versus 12 mg	g
Group from 232SM203	

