# **Subgroup Variables**

The following are defined as subgroups:

- Baseline CHOP INTEND (<= median, > median, median calculated 232SM203 ITT Set)
- Geographic region:
  - Asia-Pacific (Australia, China, Hong Kong, Japan, Lebanon, Saudi Arabia, South Korea, Taiwan, Turkey)
  - Europe (Belgium, France, Germany, Great Britain, Hungary, Italy, Poland, Russia, Spain, Sweden)
  - North America (Canada, United States)
  - o South/Central America (Brazil, Chile, Colombia, Mexico)

The main analyses for the primary endpoint and time to death and time to death or permanent ventilation for higher dose versus sham will be repeated for the subgroups: disease duration and baseline CHOP INTEND total score. Summaries of change from baseline in CHOP INTEND will be repeated for each of the three subgroups up to Day 183.

The main analyses for the change in CHOP INTEND to Day 302 and time to death and time to death or permanent ventilation will be repeated for subgroups: disease duration, baseline CHOP INTEND for the higher dose versus 12 mg comparison within 232SM203.

Summaries of change from baseline in CHOP INTEND by visit will be presented for each of the three subgroups for the higher dose versus 12 mg comparison within 232SM203.

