## Table 4: CHOP INTEND: Change from baseline to Day 183, accounting for mortality/dropout. Comparing the 50/28-mg Group to Study CS3B Sham Control

Туре	Analysis Method	Analysis Population: Further Notes	
Primary Analysis	Joint rank using multiple imputation (MI)	Matched Sham Set	
Sensitivity Analysis	Joint rank using multiple imputation (MI)	Matched Sham Set (sensitivity)	
	Joint rank using multiple imputation (MI)	Greedy matched set (sensitivity)	
	Adjustment of ranking criteria for JRT for withdrawals not due to death	Matched Sham Set	
	Adjustment of ranking criteria for JRT for permanent ventilation	Matched Sham Set	
	Subjects who died will be excluded from the MI model	Matched Sham Set	
	Joint rank using multiple imputation (MI)	Matched Sham Set. Data truncated to only include data up to Day 183 (inclusive).	
	Joint rank using Jump to Control MI	Matched Sham Set	
	Rank based implementation of joint rank method + MI	Matched Sham Set	
	Joint rank test using multiple imputation (MI), ANCOVA model not assuming equality of variance	Matched Sham Set	
	Joint rank using multiple imputation (MI) by disease duration	Matched Sham Set	
	Joint rank using multiple imputation (MI) by baseline CHOP INTEND	Matched Sham Set	
Supplementary Analysis	Trimmed mean	Matched Sham Set	

Product: Nusinersen

Study: 232SM203

Page 40

Endpoint and Comparison	Analysis Method	Analysis Population: further notes
Supplemental analysis		
Difference (50/28mg- Matched Sham Control) in change in CHOP INTEND from baseline by visit	ANCOVA using MI	Matched Sham Set
Difference (50/28mg- Matched Sham Control) in change in CHOP INTEND from baseline by visit	ANCOVA using MI (Not assuming equality of variances)	Matched Sham Set

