## 6.4.4. Change from baseline to Day 302 in CHOP INTEND total score: comparison: 50/28mg versus 12 mg Group from 232SM203.

### Main Analysis

• The change from baseline to Day 302 in CHOP INTEND total score will be analyzed using the JRT methodology to account for mortality.

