## Table 9: Change from baseline to Day 302 in CHOP INTEND total score comparison:50/28mg versus 12 mg Group from 232SM203

Туре	Analysis Method	Analysis Population: Further Notes
Main analysis	Joint rank using multiple imputation (MI)	ITT Set
Sensitivity analysis	Adjustment of ranking criteria for JRT for withdrawals not due to death	ITT Set
	Adjustment of ranking criteria for JRT for permanent ventilation	ITT Set
	Subjects who died will be excluded from the MI model	ITT Set
	Rank based implementation of joint rank method + MI	ITT Set
	Joint rank using multiple imputation (MI)	PPS Set
	Main analysis repeated using Jump to reference in the MI step	ITT Set
	Joint rank using multiple imputation (MI)	ITT Set
	by disease duration	
	Log-rank test stratified by disease duration at Screening; by baseline CHOP INTEND	ITT Set
		Analysis

Endpoint and Comparison	Analysis Method	Analysis Population: further notes
Supplemental analysis		
Difference (50/28mg- 12 mg Group from 232SM203) in change in	ANCOVA using MI	ITT Set

CHOP INTEND from baseline by visit

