### 6.4.10. Time to death (overall survival) - comparison: 50/28mg versus 12 mg Group from 232SM203

Main, sensitivity analyses will be analyzed in the same way as similar secondary endpoint described in section 6.4.8.

. .

Product: Nusinersen	Statistical Analysis Plan
Study: 232SM203	Version: 3.0 Final

....

Туре	Analysis Method	Analysis Population: further notes
Main Analysis	Log-rank test stratified by disease duration at Screening	ITT Set
Sensitivity Analysis	Cox proportional hazards with treatment and each subject's disease duration at Screening and baseline CHOP INTEND total score as terms in the model	ITT Set
	Log-rank test stratified by disease duration at Screening; by disease duration	ITT Set
	Log-rank test stratified by disease duration at Screening; by baseline CHOP INTEND	ITT Set
	Joint rank using multiple imputation (MI)	PPS Set

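### Three sensitivity or subgroup rows in the Part B infantile-onset SAP (Table 9, Table 14 and the Section 6.4.10 table) name a method that does not fit the table's endpoint

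*SAP*

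**What the plan says.** All references are to the Part B infantile-onset SAP, Version 3.0.

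**Change in CHOP INTEND to Day 302, 50/28 mg versus 12 mg (rank 5).** Section 6.4.4 sets the main analysis: "The change from baseline to Day 302 in CHOP INTEND total score will be analyzed using the JRT methodology to account for mortality". Section 3.5, Subgroup Variables, says of this comparison that "The main analyses for the change in CHOP INTEND to Day 302", together with those for the two survival endpoints, are to be run again by disease duration and by baseline CHOP INTEND. Table 9 gives the disease-duration subgroup as joint rank with multiple imputation (MI), but the baseline CHOP INTEND subgroup as "Log-rank test stratified by disease duration at Screening; by baseline CHOP INTEND".

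**Time to death or permanent ventilation (rank 10) and time to death (rank 11), 50/28 mg versus 12 mg.** Section 6.4.9 states: "Main and sensitivity analyses will be analyzed in the same way as similar secondary endpoint described in section 6.4.7". Section 6.4.10 likewise has its analyses "analyzed in the same way as similar secondary endpoint described in section 6.4.8". The main analysis in both tables is the log-rank test stratified by disease duration at Screening, on the ITT Set. The last sensitivity row of each table is "Joint rank using multiple imputation (MI"), on the Per Protocol Set (PPS). The caption of the Section 6.4.10 table is not visible in the text at hand; by position it is Table 15.

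**The concern.** A log-rank test compares event times with censoring. A change score at a fixed visit supplies neither, so the Table 9 cell does not describe an analysis of the endpoint in the table's title. Joint rank with MI, as Section 6.1 defines it, ranks a functional or NF-L score together with the time of death, and imputes that score where it is missing. A time-to-event endpoint has no such score, so the two PPS cells do not describe an analysis of their endpoints either.

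At stake is the supporting evidence around three endpoints in the sequential testing procedure: the baseline-severity subgroup for rank 5, and whatever Per Protocol check was meant for ranks 10 and 11. A programmer working from the tables alone would produce something other than what the text describes. For the two PPS rows, the text does not say what was meant.

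**Working it through.** No figure in the plan bears on this point, so the check sets the text beside the tables.

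**1. Table 9, subgroup by baseline CHOP INTEND.**
- Section 3.5: the subgroup analysis repeats the main analysis of change in CHOP INTEND to Day 302.
- Section 6.4.4: that main analysis is the joint rank test.
- Table 9, the row directly above: the disease-duration subgroup uses joint rank with MI.
- Table 4, the corresponding row for the primary endpoint: "Joint rank using multiple imputation (MI) by baseline CHOP INTEND".
- Table 9, the row in question: stratified log-rank.

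Four places agree and one cell does not. The same log-rank subgroup row also stands in Table 14 and in the Section 6.4.10 table, where it fits a time-to-event endpoint. That points to a copied row.

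**2. Table 14 and the Section 6.4.10 table, PPS row.**
- Section 6.1, Multiple imputation: MI is to be done for CHOP INTEND, HINE Section 2 total score and NF-L. No time-to-event endpoint is listed.
- Section 6.1, Joint rank methodology: the method combines a functional endpoint with mortality.
- Section 6.1, Joint rank methodology + MI: the ANCOVA on ranks adjusts for the baseline value of the endpoint. Time to death, and time to death or permanent ventilation, have no baseline value.
- Section 6.4.7: participants without an event are censored when last seen. Incomplete follow-up is not imputed.
- Sections 6.4.7 and 6.4.8, to which 6.4.9 and 6.4.10 defer: stratified log-rank, Cox, actual-treatment and subgroup analyses. There is no joint rank, no MI and no PPS analysis.
- Section 6.4.4 and Table 9: here a PPS repeat is planned in the text, and the table row for it is joint rank with MI on the PPS. The last row of the other two tables is identical to it.

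So the method does not fit the endpoint, and the survival sections plan no PPS analysis that the row could stand for. The likeliest source is again a copied row.

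**3. Extent.** Table 9 lists 8 sensitivity or subgroup rows, Table 14 lists 4 and the Section 6.4.10 table lists 4, so 8 + 4 + 4 = 16. Three of the 16 do not fit: one in each table. The main-analysis row of each table fits its endpoint and agrees with the text.

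**The case against.** Several things can fairly be said for the plan, and most of them limit the point without removing it.

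- **The Table 9 method is already fixed by the text.** Sections 3.5 and 6.4.4 together settle it as joint rank, and Table 4 shows the same pattern. This stands. A reader might infer that the test for this subgroup would be chosen only at programming, or that the subgroup analysis is lost. The document does not support that. One cell contradicts a rule that is stated elsewhere, and the cell should be brought into line.
- **The PPS rows could be run in some form.** Section 6.1 ranks deaths by time, and one variant ranks death or permanent ventilation by time, with the functional score used for everyone else. This stands as far as it goes, so saying that the rows cannot be run would be too strong. But such an analysis tests the CHOP INTEND composite, not the survival endpoint. For deaths it would repeat the PPS row already in Table 9; for permanent ventilation it would be a PPS version of another Table 9 row. The two cells name neither a functional score nor a timepoint.
- **No Per Protocol survival analysis was promised.** Apart from the disputed cells, nothing in Sections 3.5 or 6.4.7 to 6.4.10 plans one. This stands, and it means that deletion is as faithful to the text as replacement.
- **The rows were not swapped.** A reader might suppose that the log-rank and joint rank rows changed places. They did not: Table 9 has its own correct PPS row, and the two survival tables have their own log-rank rows by baseline CHOP INTEND. The faulty rows are duplicates.

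**Conclusion.** The point holds as a minor error: wrong as written in three supporting rows, one in each of three tables. The plan's own text shows that each named method does not fit the endpoint.

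Because the endpoints sit at ranks 5, 10 and 11, a reader might infer that confirmatory inference is at risk. It is not. The sequence in Section 5 (two-sided alpha of 0.05) rests on the main analyses, which are correctly specified as joint rank with MI on the ITT Set for rank 5 and stratified log-rank on the ITT Set for ranks 10 and 11. Type I error and the order of testing do not change. Only the supporting subgroup and PPS analyses are affected, and no effect on any conclusion can be put in figures from the document.

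That the rows were copied is an inference from identical or near-identical wording across the tables. The finding does not depend on it.

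**What to change.** - **Table 9, last sensitivity row:** replace the log-rank entry with joint rank using MI, by baseline CHOP INTEND, on the ITT Set. This matches Sections 3.5 and 6.4.4 and the corresponding row of Table 4.
- **Table 14 and the Section 6.4.10 table, last row:** choose one of two corrections and apply it to both. Either replace the entry with the log-rank test stratified by disease duration at Screening on the PPS, which is the direct Per Protocol repeat of the main analysis, and add a sentence saying so to Sections 6.4.9 and 6.4.10; or delete the row, which leaves the tables in agreement with Sections 6.4.7 and 6.4.8.

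The cost is three table cells, plus one sentence in each of two sections if the PPS analysis is kept. No data collection, sample size or main analysis changes. The SAP is labelled final, so the correction should go into its summary of changes, ideally before anyone has seen unblinded results.

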### 6.4.10. Time to death (overall survival) - comparison: 50/28mg versus 12 mg Group from 232SM203

Main, sensitivity analyses will be analyzed in the same way as similar secondary endpoint described in section 6.4.8.

. .

Product: Nusinersen	Statistical Analysis Plan
Study: 232SM203	Version: 3.0 Final

....

Туре	Analysis Method	Analysis Population: further notes
Main Analysis	Log-rank test stratified by disease duration at Screening	ITT Set
Sensitivity Analysis	Cox proportional hazards with treatment and each subject's disease duration at Screening and baseline CHOP INTEND total score as terms in the model	ITT Set
	Log-rank test stratified by disease duration at Screening; by disease duration	ITT Set
	Log-rank test stratified by disease duration at Screening; by baseline CHOP INTEND	ITT Set
	Joint rank using multiple imputation (MI)	PPS Set

# Joint rank using multiple imputation (MI)PPS Set6.5. Supplemental analyses supporting primary and secondary endpoints.6.5.1. Comparison: 50/28 mg Group versus CS3B sham control

The main analysis for the primary endpoint of CHOP INTEND: Change from baseline to Day 183 will be repeated for the Day 64 timepoint see table below for the specific analyses.

The Proportion of CHOP INTEND Responders at Day 183 will also be analyzed.

A subject is defined as a CHOP INTEND responder if the change from baseline in CHOP INTEND total score is greater than or equal to 4 points based on assessment at Day 183.

Subjects who die or withdraw from the study will be counted as non-responders and will be included in the denominator for the calculation of the proportion. Proportions of CHOP INTEND responders will be analyzed using logistic regression as described in the MI description in Section 6.1 and if due to low counts this is not possible then Fishers Exact test will be used.

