# 6. Efficacy Endpoints

## 6.1. General Analysis Methods for Efficacy Endpoints

## **Multiple imputation (MI)**

Product: Nusinersen	Statistical Analysis Plan
Study: 232SM203	Version: 3.0 Final

The multiple imputation method [Schafer 1997, Schafer 1999] will be used for participants who discontinue for a reason other than death or have a missing efficacy result at the timepoint of interest. This will be performed for CHOP INTEND, HINE Section 2 total score and NF-L. Any imputation on an item level within a scale for CHOP INTEND and HINE section 2 will be performed prior to performing MI.

The imputations will be performed on total scores. All available data will be used i.e., where subjects have missed doses but continued to perform assessments; otherwise, any missing values will be imputed using MI. In a situation where historical data is used as the control group only the visits which are common between the two groups will be utilized. For example, for the CS3B sham control versus higher dose comparison only the Day 64, Day 183 and Day 302 visits will be included in the list of post baseline visits.

In this situation if convergence issues occur then only the Day 64 and Day 183 post baseline visits will be included.

The Markov Chain Monte Carlo (MCMC) method will be used to impute the missing score.

The treatment variable will be coded so that the Higher dose group is the first in the sort order. Prior to the Proc MI step the dataset will be sorted by treatment and then ascending unique subject identifier (USUBJID). The variable list in the model for imputations will include:

- treatment group, disease duration, baseline value for the endpoint, and all available post baseline values
- For NF-L, the log of baseline and post-baseline values will be used in the PROC MI step.

A set of 100 complete imputed datasets will be generated and the relative efficiency parameter will also be checked to determine the acceptability of the imputed results i.e. it should be close to 98% or higher. The seed used for the multiple imputation for CHOP INTEND will be 5846892, for HINE section 2 Motor Milestones will be 8746890 and for NF-L will be 7635789.

If the MI procedure imputes any values outside the expected range for the scale, e.g. from 0 to 64 for CHOP INTEND, then values below 0 will be set to 0 and values above 64 will be set to be 64. For NF-L if any imputed values are  $< \log(LLOQ)$  then set as  $\log(LLOQ/2)$ .

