## **Responder Analyses of CHOP INTEND and HINE Section 2**

Product: Nusinersen	Statistical Analysis Plan
Study: 232SM203	Version: 3.0 Final

For CHOP INTEND it is planned to use multiple imputation to deal with missing data and the analysis will be performed using logistic regression. Should the number of responders be less than 5 in either group, Fisher's exact test will be used instead. In this scenario, it will not be possible to use multiple imputation and the following approach will be implemented to impute a missing response:

For a given timepoint such as Day 183, subjects who die or withdraw from the study prior to Day 183 will be counted as non-responders and will be included in the denominator for the calculation of the proportion of responders. In determining the response at Day 183 where a subject has missing response but the two immediate flanking visits both have an evaluable response an imputation will be performed. For example, the visit of interest is Day 183 and the immediate flanking visits are Day 135 and Day 279. If at both Day 135 and Day 279 the subject is a responder, then an imputation will be performed to count the missing Day 183 as a responder. For any other combination of missing/non response observed in flanking visits the subject will be considered a non-responder.

For HINE Section 2 motor milestone responders it is not planned to use multiple imputation. Therefore, if the endpoint is at Day 302 and the participants has a missing HINE Section 2 response, they will be considered to be a non-responder. In a situation where the endpoint is at Day 183 and flanking visits may be available the imputation approach described above for CHOP INTEND response will be implemented.

[figure not shown]

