### 6.5.2. Comparison: 50/28mg versus 12 mg Group from 232SM203

For the comparison of higher dose and 12 mg Group from 232SM203, some of the secondary endpoints will be repeated as listed below, also the proportion of CHOP INTEND responders at Day 183 and Day 302 and proportion of Motor Milestones responders at Day 302 will be analyzed.

Endpoint Ar	alysis Method	Analysis Population: further notes
Change in CHOP INTEND from baseline to Day 18.	3 Joint rank using multiple imputation (MI)	ITT set Repeat for Day 29 and 64.
Change in Motor Milestones total score from baselin to Day 183	e Joint rank using multiple imputation (MI)	ITT set
The Proportion of CHOP INTEND Responders at Da 183	ay Logistic regression or Fisher's Exact Test	ITT set

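### A withdrawn infant can be imputed as a CHOP INTEND responder against 12 mg but is a non-responder against sham, because Sections 6.1, 6.5.1 and 6.5.2 do not share one rule

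*SAP*

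**What the plan says.** All references are to the Part B infantile-onset SAP unless stated.

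- **Section 6.1, Multiple imputation.** Imputation "will be used for participants who discontinue for a reason other than death or have a missing efficacy result at the timepoint of interest". A withdrawal for another reason is therefore imputed; a death is outside the rule.
- **Section 6.1, Responder Analyses.** The main route is: "For CHOP INTEND it is planned to use multiple imputation to deal with missing data and the analysis will be performed using logistic regression". The fallback is Fisher's exact test: "Should the number of responders be less than 5 in either group". The text then says "In this scenario, it will not be possible to use multiple imputation", and only after that sentence comes the scoring rule, "subjects who die or withdraw from the study prior to Day 183 will be counted as non-responders", with these infants kept in the denominator.
- **Section 6.5.1 (versus CS3B sham).** Response is a gain of at least 4 points at Day 183. Then: "Subjects who die or withdraw from the study will be counted as non-responders". The next sentence reads "Proportions of CHOP INTEND responders will be analyzed using logistic regression as described in the MI description in Section 6.1", with Fisher's test if counts are too low.
- **Section 6.5.2 and Table 17 (versus 12 mg).** These add "the proportion of CHOP INTEND responders at Day 183 and Day 302", by logistic regression or Fisher's test. They give neither a definition of response nor a rule for deaths or withdrawals.
- **Section 6.1, Joint rank methodology + MI.** Infants who died stay in the imputation model. Values generated after death are barred from the rank score; the responder analyses are not mentioned.

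**The concern.** The same event, leaving the study alive before the visit, is scored in two ways. Section 6.1 makes it non-response only in the fallback; Section 6.5.1 makes it non-response without that limit, while citing the imputation method that would fill the value in. Section 6.5.2 is silent, so the general method in 6.1 is the written default.

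Three things follow from a literal reading:

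- A withdrawn infant on 50/28 mg is a non-responder against sham, yet can be an imputed responder against 12 mg.
- Under 6.1, the meaning of response for a withdrawn infant depends on the data: crossing 5 responders in a group changes both the test and the scoring.
- Table 17 would hold two responder endpoints with opposite handling. For HINE Section 2 response, 6.1 rules out multiple imputation and scores a missing Day 302 result as non-response.

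At stake is a reported dose comparison whose estimate depends on a choice left open until after unblinding.

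**Working it through.** **Step 1. The rules side by side.**

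| Infant's status at the visit | 6.1, logistic | 6.1, Fisher | 6.5.1 (sham) | 6.5.2 (12 mg) |
|---|---|---|---|---|
| Withdrew alive | Imputed | Non-responder | Non-responder, either route | No rule; 6.1 by default |
| Died | Outside the imputation rule; scoring not stated | Non-responder | Non-responder, either route | Not stated on the logistic route |
| On study, score missing | Imputed | Flanking-visit rule | As 6.1 | As 6.1 |

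The first row is the conflict. The second row is a gap, not a direction to impute.

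**Step 2. Size.** The SAP gives no response rate or power for these analyses, so there is no figure to reproduce.

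Inputs:
- Losses of 4 of 50 on 50/28 mg and 5 of 25 on 12 mg, from the hypothetical trimmed-mean example in Section 6.1. It pools deaths and withdrawals.
- p1 and p2, the response rates among completers on 50/28 mg and 12 mg: assumed.
- q, the chance that a lost infant is imputed as a responder: 0 under non-responder scoring, equal to p if imputed like a completer.

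Formula: rate = (completers × p + lost × q) / N.

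- With q = 0: 46 × p1 / 50 = 0.92 p1, and 20 × p2 / 25 = 0.80 p2.
- With q = p: p1 and p2.
- Shift = (0.92 p1 − 0.80 p2) − (p1 − p2) = 0.20 p2 − 0.08 p1. With p1 = p2 = p this is 0.12 p.

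| Completer response, 50/28 mg v 12 mg | Non-responder scoring | Imputed like completers | Shift |
|---|---|---|---|
| 50% v 50% | 46.0% v 40.0%, diff. 6.0 | 0 | 6.0 points |
| 80% v 80% | 73.6% v 64.0%, diff. 9.6 | 0 | 9.6 points |
| 90% v 90% | 82.8% v 72.0%, diff. 10.8 | 0 | 10.8 points |
| 85% v 70% | 78.2% v 56.0%, diff. 22.2 | 15.0 | 7.2 points |

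**Step 3. How firm the range is.**
- If lost infants are imputed at half the completers' rate (p = 0.8, q = 0.4), the arms are 76.8% v 72.0%, a difference of 4.8, so the shift is 9.6 − 4.8 = 4.8 points.
- If a fraction f of the losses in each arm are withdrawals and the rest are deaths scored as non-response, the shift is f × 0.12 p, so smaller.
- If deaths fall unevenly, this ceiling does not hold. With all 4 losses on 50/28 mg deaths and all 5 on 12 mg withdrawals, the shift is 0.20 p, or 10 to 18 points for p of 0.5 to 0.9. With the reverse it is −0.08 p, or 4.0 to 7.2 points the other way.

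**The case against.** **Section 6.5.1 can be read without contradiction.** Section 6.1 is general and 6.5.1 is specific to the endpoint: death or withdrawal is non-response, and imputation fills gaps for infants still on study. The Part B later-onset SAP does exactly this for the 3-point HFMSE response, setting the imputed value aside for early terminators. This stands for 6.5.1 taken alone. It does not settle 6.5.2.

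**Section 6.5.2 must borrow from 6.5.1.** The 4-point threshold appears only there, so a reader may carry over the next sentence too. That is plausible and would remove the difference between comparisons, but it is not written. Section 6.5.1 is headed for the sham comparison and its threshold is tied to Day 183.

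**Two stronger readings are not supported.**
- A reader might infer that a dead infant can count as a responder against 12 mg, since deaths stay in the imputation model and the discard sentence mentions only ranks. But the general rule confines imputation to reasons other than death, and no text turns a post-death value into a response. The handling is unstated, no more.
- A reader might infer that Day 183 and Day 302 are scored differently. Table 17 gives both visits the same methods. They would differ only if one visit alone had fewer than 5 responders in a group.

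**The size is illustrative and the stakes are limited.** The losses are hypothetical, the response rates are assumed, and the actual model conditions on treatment, disease duration, baseline and all available scores. The 11 ranked tests in Section 5, Table 2, include no CHOP INTEND responder analysis. All of this stands and limits the severity.

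**Conclusion.** The point holds in a limited form. For infants who withdraw alive, Sections 6.1 and 6.5.1 differ on the logistic route, and 6.5.2 does not say which applies. By default a withdrawal can be an imputed response against 12 mg and is non-response against sham, and under 6.1 the scoring depends on whether a group has fewer than 5 responders. Deaths in the 6.5.2 logistic model have no stated handling.

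On the SAP's hypothetical losses, with equal completer response of 50% to 90%, the choice moves the between-arm difference by up to 6.0 to 10.8 points (7.2 with 85% v 70%). This assumes that every loss is a withdrawal imputed at the completers' rate; it is a ceiling if deaths make up a similar share of losses in both arms. No alpha, primary result or ranked result is affected. The rule should still be fixed before unblinding, because it changes a reported estimate and not just the wording.

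**What to change.** State one rule in Section 6.1, Responder Analyses, for the logistic and Fisher routes, both comparisons, and Day 183 and Day 302:

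- Death or study withdrawal before the visit is non-response, and the infant stays in the denominator.
- Multiple imputation is used only for infants alive and on study with a missing score. On the Fisher route the existing flanking-visit rule continues to serve these infants.

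Section 6.5.2 and Table 17 should refer to this rule and to the 4-point definition, stated for Day 302 as well as Day 183. This agrees with the SAP's handling of HINE Section 2 response (6.1 and 6.4.1) and CGIC (6.6.3), and with HFMSE response in the later-onset SAP. If the sponsor prefers to impute withdrawals, 6.5.1 must be amended instead and deaths addressed explicitly.

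The cost is SAP wording. Response rates fall slightly. The between-arm difference may widen, as in the worked example where 12 mg loses more infants, or narrow: with 10% lost in each arm and completer response of 80% v 60%, it goes from 20 points to 0.90 × 20 = 18 points.
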